### Introduction

Older multimorbid patients with hip fractures are a growing patient population due to demographic developments in western industrial nations. Hospital mortality increases with anesthesia risk and ranges from less than 1% (ASA (American Society of Anesthesiologists) Physical Status 1) to 50% (ASA PP 5). This presents the team with a number of challenges when patients are at high risk of anesthesia (ASA PP 3-4, associated hospital mortality 5-20%).

Surgical treatment can be performed under general or spinal anesthesia. Additional peripheral nerve blocks contribute to perioperative pain therapy.

The aim of the study is to demonstrate that the surgical treatment of proximal femoral fractures is possible using a peripheral regional anesthesia procedure.

Both spinal and general anesthesia can contribute to side effects such as postoperative delirium or circulatory instability. We postulate that these side effects occur less frequently when the procedure is performed under peripheral regional anesthesia.

We perform a double injection technique (dual-guidance concept: ultrasound and nerve stimulation). The first injection targets the sacral plexus under the piriformis muscle.

A second injection targets the lumbar plexus: psoas-compartment-block (segments L2-L4) and transmuscular quadratus-lumborum block (segments Th12-L1).

### Study design

single-center, prospective

### Study goal

## Health economic goals

We expect the study results to improve the safety of multimorbid elderly patients undergoing hip fracture surgery.

## Interventions

Intervention A	20ml ropivacaine 0.375% (parasacral sciatic nerve block)
Intervention B	20ml ropivacaine 0.375% (psoas-compartment block)
Intervention C	20ml ropivacaine 0.375% (transmuscular quadratus-lumborum block)
Intervention D	Supplemental analgesic (sufentanil) and/or sedative (propofol) medication

## Patient population

Adult men and women undergoing surgical treatment of proximal femoral fractures.

## Study center

HELIOS Medical Center Schwerin, Germany

## Schedule

12-18 months

## **1. Introduction**

Both general and spinal anaesthesia are established anaesthesia procedures for the surgical treatment of proximal femoral fractures. Additional peripheral nerve blockades are performed with the aim of perioperative analgesia.

## **2. Primary and secondary outcome parameters**

With the present prospective study design, we examine whether the surgical treatment of proximal femoral fractures exclusively under peripheral regional anaesthesia (blockade of the lumbosacral plexus) is a reliable anesthesia procedure. The main objective is to determine the frequency of necessary supplementation by analgesics/sedatives (criterion 1) or the conversion rate (criterion 2) to general anaesthesia (infra- or supraglottic airway). Side effects (e.g. delirium and pneumonia rates), hospital length of stay and hospital mortality are recorded.

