## **3. Study design**

This is a single-center prospective study.

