## **8. Dropout of patients**

The non-intervention-related reasons for a drop-out include in particular the withdrawal of the patient's consent and the subsequent disclosure of exclusion criteria (e.g. participation in another clinical trial).

Drop-outs caused by the study intervention are e.g. severe cardiovascular complications (cardiac arrest, shock, threatening arrhythmias) due to the systemic toxicity of the local anaesthetic.

If necessary, regional anesthesia is supplemented by the administration of analgesics and sedatives or general anesthesia is performed. The time and dose of the narcotics are documented and the procedure is performed as planned without the patient being excluded from the study.

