### **Final Version**

**Date 29.06.2019**

## **Statistical Analysis Plan**

The metric parameters are described by mean value (Mw) and standard deviation (Sd). The Mann-Whitney U test tests whether the two groups differ in the distribution of the parameter. If the p-value of the test is less than the selected significance level (0.05), then the groups differ significantly in terms of distribution.

Categorical parameters (0/1) are described by the exact Fisher test. The exact Fisher test examines whether each parameter is independent of its membership in a group. If the p-value of the test is less than the selected significance level (0.05), then there is a significant dependence. The two groups then differ significantly with respect to the selected parameter.

The incidence of adverse events in the two groups is described with odds ratios (95% confidence interval).

Statistical analyses were performed bilaterally, using GraphPad PRISM 8.0 (GraphPad Software Inc., San Diego, CA, USA).

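### The main objective is a frequency, but the SAP plans only two-group comparisons, with no interval for that frequency and no stated denominator

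*Protocol*

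**What the plan says.** **The question.** Protocol section 2 asks whether operating on proximal femoral fractures "exclusively under peripheral regional anaesthesia (blockade of the lumbosacral plexus) is a reliable anesthesia procedure". It then sets the target: "The main objective is to determine the frequency of necessary supplementation by analgesics/sedatives (criterion 1) or the conversion rate (criterion 2) to general anaesthesia".

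**The design.** Protocol section 3 says only: "This is a single-center prospective study". Section 6.2 gives each patient a number and describes no allocation. Section 6.4 describes one set of three blocks for everyone.

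**The analysis.** Protocol section 9 refers all statistics to the SAP. For binary outcomes the SAP says: "Categorical parameters (0/1) are described by the exact Fisher test". It explains: "The exact Fisher test examines whether each parameter is independent of its membership in a group". Its only interval belongs to another quantity: "The incidence of adverse events in the two groups is described with odds ratios", with 95% confidence limits. The SAP names neither criterion and no analysis set.

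**The denominator.** Protocol section 8 keeps supplemented and converted patients in the study. It puts toxicity events in a different class: "Drop-outs caused by the study intervention are e.g. severe cardiovascular complications". A further class begins: "The non-intervention-related reasons for a drop-out include in particular the withdrawal" of consent, and also covers exclusion criteria that come to light later. The section does not say how either class of drop-out is analysed.

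**The concern.** The study sets out to determine how often the block is not enough. The natural result is a proportion with a confidence interval, on a denominator fixed in advance. The SAP supplies a test and an odds ratio, both of which need a comparison group that the supplied protocol does not describe. Followed literally, the plan gives no statement of precision for its own main objective.

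The denominator matters because a toxic reaction to the local anaesthetic is a failure of the method under study. If such patients could be left out of the reliability figure, the figure would move in favour of the block. With no rule written beforehand, the choice of proportion, interval and denominator could be made after the data are seen.

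**Working it through.** The documents state no sample size, expected rate, target rate or precision, so there is no planned figure to reproduce. All counts and rates below are assumptions for illustration.

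**1. What the planned methods return.** With one group, the 2×2 table of group by outcome has an empty row. Take an assumed 35 patients supplemented or converted and 65 block-alone:

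| | Supplemented or converted | Block alone |
|---|---|---|
| Study patients | 35 | 65 |
| Second group | 0 | 0 |

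- Odds ratio = (35 × 0)/(65 × 0) = 0/0, which is undefined.
- Fisher's test: given the margins only one table is possible, so p = 1 whatever the data.

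If a second group did exist, the p-value would address a difference between groups. It would still give no interval for the frequency in the block patients.

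**2. What a one-sample interval would add.** Exact (Clopper-Pearson) 95% limits for an assumed block-alone proportion of 80%:

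| Block alone / n | Exact 95% CI |
|---|---|
| 24/30 | 61.4 to 92.3% |
| 40/50 | 66.3 to 90.0% |
| 80/100 | 70.8 to 87.3% |

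The same 80% supports quite different conclusions about reliability depending on n. The plan has nothing that would show this.

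**3. Effect of the denominator.** Let x be the number block-alone, n the number of blocks started, and d the number of intervention-caused drop-outs removed, none of them managed under the block alone. The proportion changes from x/n to x/(n − d). With x = 65 and n = 100:

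| d | Proportion | Exact 95% CI |
|---|---|---|
| 0 | 65/100 = 65.0% | 54.8 to 74.3% |
| 1 | 65/99 = 65.7% | 55.4 to 74.9% |
| 2 | 65/98 = 66.3% | 56.1 to 75.6% |
| 5 | 65/95 = 68.4% | 58.1 to 77.6% |

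Two removals move the estimate by 66.3 − 65.0 = 1.3 points, well inside the sampling uncertainty. The direction depends on the assumption stated: removing one patient who had been managed under the block alone would give 64/99 = 64.6%.

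**4. Overlap of the two criteria.** Let C1 be the supplementation rate and C2 the conversion rate, with C1 + C2 at most 1 and all patients operated on. If only these two rates were reported, the block-alone proportion would lie between 1 − C1 − C2 and 1 − max(C1, C2), a width of min(C1, C2). With C1 = 30%:

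- C2 = 5%: 65 to 70%.
- C2 = 20%: 50 to 70%.

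A cross-tabulation removes this gap entirely.

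**The case against.** **The estimate is implicit.** Each criterion is a plain count, and a Fisher test needs the counts, so the proportion can be worked out. That stands. What is missing is the interval, the denominator, and any statement that the proportion is the primary result.

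**The plan does not say that patients harmed by the block are removed.** A reader might infer this from the label of drop-out, especially as section 8 expressly keeps supplemented and converted patients. The documents do not support that inference: section 8 is silent on how drop-outs are analysed. Sections 7.3 and 7.4 require complications to be documented and serious events reported to the ethics committee, so these patients would be on record. The point is an open rule, not a planned exclusion.

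**The block-alone proportion is not necessarily lost.** A reader might infer that two criteria joined by *or* leave it undeterminable. The *or* can also be read as one composite, whose complement is the block-alone proportion. Section 8 has time and dose documented, so the overlap should be recoverable. Nothing says that only the two separate rates will be reported. This part is a clarification.

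**Supplementation may be part of the technique.** The protocol's Interventions summary lists supplemental sufentanil and/or propofol as Intervention D, so a supplemented patient is not plainly a failure. This is a fair reason to report each criterion separately beside the composite. It is also a reason to keep section 2's restriction to *necessary* supplementation. It does not supply an interval or a denominator.

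**The preparatory sufentanil does not make every patient supplemented.** Section 6.3 gives it before the block as routine preparation, so it most naturally falls outside criterion 1, although no section says so.

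**Conclusion.** The concern holds for the analysis method. The main objective is a frequency, the SAP offers only two-group comparisons for binary outcomes, and the supplied protocol describes no second group. This conclusion rests on no assumed rate.

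The denominator part is conditional. Excluding intervention-caused drop-outs would favour the block if those patients were not managed under the block alone. On the assumed 65 of 100, the gain is 0.7 points for one event and 1.3 points for two. It reaches 3.4 points only with five, a frequency that nothing in the documents supports. Overlap between the criteria is a minor matter that a cross-tabulation settles.

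The change should be made because it affects the main result and costs little. Its numerical effect may be modest and cannot be determined from the documents. The case report form was not supplied; it may record the overlap, but recording data does not specify an analysis.

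**What to change.** In the SAP, state as the primary analysis three proportions, each with an exact (Clopper-Pearson) 95% interval:

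1. patients with necessary supplementation;
2. patients converted to general anaesthesia;
3. patients with neither (block alone).

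**Counting.** A patient with both events counts in both criteria and once in the composite. Show the 2×2 cross-tabulation.

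**Denominator.** Use all patients in whom the block was started, including the intervention-caused drop-outs of protocol section 8. A patient whose surgery did not go ahead because of such an event counts as not block-alone. Patients who leave after block start for other reasons stay in the denominator unless consent to use their data is withdrawn, and are listed with reasons. This avoids exclusions made once the outcome is known.

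**Definitions.** Keep section 2's restriction to *necessary* supplementation and its definition of conversion. Report any supplemental dose, necessary or not, as a sensitivity result. Report any other change of anaesthetic method separately and not as block-alone. Report the preparatory sufentanil of section 6.3 descriptively.

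**Cost.** A few lines in the SAP; nothing given to patients changes. The sponsor should check that the case report form captures the items needed. The composite failure rate may be higher than either criterion alone, because a patient who meets either one counts.

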## **3. Study design**

This is a single-center prospective study.

## **4. Schedule**

The estimated recruitment schedule is approximately 12-18 months.

## **5. Patient population**

### **5.1. Inclusion criteria**

The following inclusion criteria must be met :

- Surgical treatment of proximal femoral fractures
- Age over 18 years
- Written informed consent

### **5.2. Exclusion criteria**

Patients who meet one or more of the following criteria may not be included in the trial:

 **pdf element**  
Die Trial Version  
- Local and systemic signs of inflammation  
- Known allergy to used local anaesthetics  
- Participation in other studies

- Obesity from grade 2 (BMI>35)
- periprosthetic fractures- known persistent drug, drug or alcohol abuse

### **5.3. Co-morbidities**

Preexisting co-morbidities are documented in the patient record.

### **5.4. Co-medication**

All medications that are given in addition to the study medication are considered concomitant and are documented in the patient record (especially medications that have an inhibitory effect on the coagulation system).

## **6. Study protocol**

### **6.1. Recruitment**

The patients are recruited in the context of anesthesiological preparation. Patients who have confirmed their participation in the exam by written informed consent will first be clinically evaluated. If the patient meets all inclusion and no exclusion criteria, the patient is enrolled in the study.

### **6.2. Allocation of the study medication**

After admission to the study, each patient receives a patient number, which is noted on the Case Report Form (CRF).

### **6.3. Monitoring and preoperative preparation**

Patients are initially treated in the context of normal preoperative preparation. This includes the installation of a peripheral-venous access with connection of 1000ml balanced electrolyte solution. After connection of an oxygen nasal probe (2 l/min oxygen) and administration of 5-10 µg Sufentanil the patients are placed on the non-fractured side.

The following parameters are monitored until complete postoperative recovery:

The parameters are documented in the anesthesia protocol. The minimum/maximum blood pressure and the need for circulatory drugs are recorded in the Patient Documentation Form.

#### **6.4. Interventions**

The ultrasound-guided regional anesthesia is performed by two experienced anesthetists. We use a Sonosite (EDGE) ultrasound device with convex transducer (C60 2-5MHz) and a Pajunk 21G-100mm Sonoplex needle in in-plane technique. At the same time, the needle position is confirmed by nerve stimulation (dual guidance concept). For this purpose we use a Stimuplex HNS12 from Braun, Melsungen, Germany (frequency 2Hz, pulse width 0.1ms, stimulation limit <1mA).

Double injection technique with three (1a-c) target structures. (Resulting Anaesthesia level Th12-S3)

Intervention 1a      20ml Ropivacaine 0.375%. Parasacral ischiadicus block (18)  
Segments L4-S3

Intervention 1b      20ml Ropivacaine 0.375% Psoas compartment block (16)  
Segments L2-L4

Intervention 1c      20ml Ropivacaine 0.375% transmuscular quadratus-lumborum block (20) Segments T12-L1

#### **6.5. Follow-up**

Patients are initially cared for in the postoperative anesthesia care-unit (PACU). Depending on the clinical condition of the patients, further care is provided either at the normal ward or on an intensive care unit. For all study patients, a daily clinical visit is made until discharge.

#### **6.7. Health economic assessment**

Peripheral regional anesthesia expands the spectrum of possible anesthesia for proximal femoral fractures. The procedure can contribute to the reduction of perioperative complications, especially in cases where there is a high risk of anesthesia.

## 7. Adverse events

### 7.1. Adverse events due to the local anesthetic

#### Allergic reaction

Allergic reactions are very rare in amide-type topical anesthetics and are mostly due to the methylparaben preservative contained in larger packs (e.g., 50ml bottles).

#### Local toxicity

There are no major studies on local-toxic effects of prilocaine or ropivacaine. Possible would be a disturbance of the periaxonal milieu or the nervous blood supply (compartment effect of the local anesthetic depot). Neurological complications occurred after hyperbaric lidocaine was continuously administered intrathecally with 7.5% glucose. Similar observations were not made for peripheral nerve blocks.

#### Systemic toxicity

Systemic toxicity occurs at high plasma levels by intravascular injection or absolute or relative overdose with rapid resorption of the local anesthetic from the site of action.

The cerebral tendency to seizure is increased by the local anesthetic effect on inhibitory cortical centers. With or without preconvulsive warning signs (numbness of the tongue and perioral, metal taste, slurred speech, ear blades, blurred vision, restlessness), generalized convulsions occur. With rising plasma levels, coma and respiratory paralysis can occur.

Inhibition of intracellular ATP production and blockade of sodium channels (vasal, cardiac, sympathetic) results in hypotension and variable cardiac arrhythmias (bradycardia to asystole, ventricular arrhythmias to ventricular fibrillation).

### 7.2. Adverse events due to the peripheral nerve block

Nerve lesions may be due to needle trauma (vascular or nerve lesion) or as a result of improper positioning on the operating table. In addition, side effects may occur as a result of the stress situation: vagally mediated bradycardias (syncope) or anxiety episodes with hypertonic and/or tachycardic circulatory conditions.

### **7.3. Evaluation of adverse events**

Ropivacaine is a drug approved for peripheral nerve blocks that we use within the maximum permitted dose and indication. All occurring complications are documented and the likelihood of the causal relationship with the regional anaesthesia procedure is stated. Since this is a standard regional anaesthesia procedure, it can not be expected that previously unknown complications will occur.

### **7.4. Information to the ethics committee**

In accordance with the GCP Regulation, any severe adverse event (SAE) or unexpected (SUSAR) adverse event occurring during the trial that could affect the safety of the subjects or the conduct of the trial will be reported to the relevant local ethics committee. The report is issued by the principal investigator.

Non-serious adverse events are documented in the Patient Documentation Sheet (CRF)

## **8. Dropout of patients**

The non-intervention-related reasons for a drop-out include in particular the withdrawal of the patient's consent and the subsequent disclosure of exclusion criteria (e.g. participation in another clinical trial).

Drop-outs caused by the study intervention are e.g. severe cardiovascular complications (cardiac arrest, shock, threatening arrhythmias) due to the systemic toxicity of the local anaesthetic.

If necessary, regional anesthesia is supplemented by the administration of analgesics and sedatives or general anesthesia is performed. The time and dose of the narcotics are documented and the procedure is performed as planned without the patient being excluded from the study.

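### Section 8 lets a late-found exclusion criterion remove a patient at any time, including after the block and after outcomes are seen, so the recorded side-effect rates can be biased downward

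*Protocol*

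**What the plan says.** **Eligibility.** Protocol section 6.1 judges eligibility before entry: "If the patient meets all inclusion and no exclusion criteria, the patient is enrolled in the study". The exclusion criteria in section 5.2 include "Local and systemic signs of inflammation", with no cut-off and no time of assessment, and "known persistent drug, drug or alcohol abuse".

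**Drop-out.** Section 8 opens its first group of reasons with "The non-intervention-related reasons for a drop-out include in particular the withdrawal of the patient's consent" and adds "the subsequent disclosure of exclusion criteria (e.g. participation in another clinical trial"). A second group is tied to the intervention: "Drop-outs caused by the study intervention are e.g. severe cardiovascular complications (cardiac arrest, shock, threatening arrhythmias"), attributed to systemic toxicity of the local anaesthetic. Patients who need supplementary drugs or general anaesthesia are treated differently: their operation goes ahead and they are explicitly kept in the study.

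**Outcomes and follow-up.** Section 2 makes supplementation and conversion the main objective (criteria 1 and 2) and continues: "Side effects (e.g. delirium and pneumonia rates), hospital length of stay and hospital mortality are recorded". Section 6.5 provides that "For all study patients, a daily clinical visit is made until discharge".

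**Analysis.** The SAP reports adverse events in two groups as odds ratios with 95% confidence intervals. It names no analysis set, no denominator and no rule for drop-outs or missing data.

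**The concern.** Removing a patient who turns out to be ineligible is harmless when the discovery has nothing to do with the outcome. Participation in another trial, the only example section 8 gives, is probably of that kind. Two other criteria in section 5.2 may not be. A patient who becomes delirious may have the alcohol and drug history taken again. A patient who develops pneumonia may have the preoperative findings re-read for inflammation that was already there. A patient with the same baseline facts and a smooth course gives nobody a reason to look. The criterion is then a baseline fact, but its discovery depends on the outcome.

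If such patients leave the analysis, cases go from the numerator while comparable uneventful patients stay in the denominator, and the technique looks safer than it is. Delirium and pneumonia are the outcomes most directly exposed. Length of stay and hospital mortality could be affected in the same way. Because section 8 labels these drop-outs as unrelated to the intervention, a reader of the results would have little reason to question them.

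**Working it through.** **Step 1: can removal happen after the block?** Section 6.1 settles eligibility before enrolment, so a later disclosure must fall after enrolment. Section 8 sets no end to that period, and section 6.5 follows patients until discharge. Disclosure after surgery is therefore within the rule, although the text does not mention it.

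**Step 2: does a drop-out leave the analysis?** This is not stated outright. Section 8 needs to say that supplemented or converted patients remain in the study only if drop-outs do not. The SAP contains nothing that would bring them back.

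**Step 3: direction and size.** The documents give no sample size, event rate or drop-out rate, so there is no stated figure to reproduce. All inputs below are assumptions.

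- p = true event rate
- f1 = share of patients with the event who are removed
- f0 = share of patients without the event who are removed

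Observed rate = p(1 − f1) / [p(1 − f1) + (1 − p)(1 − f0)]

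It follows that the odds of the event are multiplied by (1 − f1)/(1 − f0).

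For p = 20% and f0 = 2%:

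- f1 = 10%: 0.180 / (0.180 + 0.784) = 18.7%
- f1 = 20%: 0.160 / (0.160 + 0.784) = 16.9%
- f1 = 30%: 0.140 / (0.140 + 0.784) = 15.2%

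Other true rates, again with f0 = 2%:

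| True rate | f1 = 10% | f1 = 20% | f1 = 30% |
|---|---|---|---|
| 20% | 18.7% | 16.9% | 15.2% |
| 10% | 9.3% | 8.3% | 7.4% |
| 5% | 4.6% | 4.1% | 3.6% |
| Odds multiplied by | 0.90/0.98 = 0.918 | 0.80/0.98 = 0.816 | 0.70/0.98 = 0.714 |

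**Step 4: when the bias is absent or reversed.** With f1 = f0 = 2% the multiplier is 1 and the observed rate equals p. With f1 = 2% and f0 = 10%, a true 20% appears as 0.196 / (0.196 + 0.720) = 21.4%. The rate is too low only if f1 exceeds f0.

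**Step 5: effect of the fix.** If nobody is removed once the block has been started, f1 = f0 = 0 and the observed rate equals p. This bias is then zero whatever the true rate.

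**The case against.** The strongest reply is that the route is narrower than it looks, and much of that reply stands.

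- **Substance abuse.** The criterion covers *known* abuse. A reader might infer that abuse first discovered through a postoperative delirium would lead to removal. On its natural reading the criterion does not cover that patient. What remains is abuse already known, for example to the family or an earlier physician, that was missed at screening.
- **Inflammation.** A reader might also infer that the inflammation of a postoperative pneumonia could itself disqualify a patient. It is an outcome, not a baseline criterion. The route needs inflammation that was present before the block and overlooked.
- **Data handling.** Section 8 does not say that a drop-out's data are discarded, and section 7.3 requires all complications to be documented. But documenting an event does not place the patient in the denominator of a reported rate, and the SAP does not say who is in it.
- **Main objective.** Patients who are supplemented or converted are kept, so the argument bears mainly on the side-effect outcomes, length of stay and mortality.
- **Comparison.** It is tempting to say that the rule acts on one group only, because only study patients are screened against these criteria. The documents do not support this: neither defines the two groups or says how the second was screened. The effect on the odds ratio depends on whether the rule is applied equally in both.

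These points limit how often the problem can arise and how firmly its effect can be stated. They do not close the gap, because a rule without a time limit still allows removal once the outcome is known.

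**Conclusion.** The point holds as a risk that the plan leaves open. The documents do not show that the reported rates will in fact be too low, and that stronger statement should not be made. A downward bias needs three things: disclosure after the event, which the text permits but does not describe; removal from the analysis, which section 8 implies and the SAP does not contradict; and more frequent discovery among patients with the event, which is plausible but assumed.

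The size cannot be computed from the documents. The illustrated losses at a true rate of 20% run from 1.3 to 4.8 percentage points and rest wholly on the assumed removal shares; equal shares give none.

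The intervention-related drop-outs in section 8 deserve the same attention. There, removal is tied to a severe adverse outcome directly, with no need for an argument about discovery. One rule on who is analysed settles both. The change is worth making because it is cheap and replaces a rule open to outcome-dependent removal.

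**What to change.** State in section 8 and in the SAP that:

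1. every patient in whom the block was started stays in the analysis of criteria 1 and 2, side effects, length of stay and mortality, including patients with a later-found exclusion criterion and those listed as intervention-related drop-outs;
2. removal from the analysis for ineligibility is allowed only before the first injection;
3. exclusion criteria found later are reported as protocol deviations, and the analysis is repeated without those patients as a sensitivity analysis;
4. only withdrawal of consent to the use of data removes data.

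This concerns who is analysed and does not alter clinical care. It costs a short paragraph in each document and one sensitivity table, with no extra patients; the daily visits in section 6.5 already run to discharge. The small downside is that the primary analysis will include a few ineligible patients, and the sensitivity analysis shows how much they matter.

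### Protocol section 8 classes severe cardiovascular toxicity of the block as a drop-out, and neither document says that these patients stay in the analysed denominators

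*Protocol*

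**What the plan says.** Protocol section 8 has three short paragraphs. The first gives drop-out reasons unrelated to the intervention, such as withdrawn consent. The second reads "Drop-outs caused by the study intervention are e.g. severe cardiovascular complications (cardiac arrest, shock, threatening arrhythmias") and attributes these events as "due to the systemic toxicity of the local anaesthetic". The third covers patients who need extra analgesics or sedatives or a general anaesthetic; for them, "the procedure is performed as planned without the patient being excluded from the study". No such assurance is given for the patients in the second paragraph.

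Section 7.3 secures the record of events: "All occurring complications are documented and the likelihood of the causal relationship with the regional anaesthesia procedure is stated". Section 7.4 sends severe events that could affect safety or trial conduct to the ethics committee, and section 6.5 plans daily visits to all study patients until discharge.

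Section 9 leaves the statistical methods to the SAP. The SAP's statement on harms is "The incidence of adverse events in the two groups is described with odds ratios (95% confidence interval"). It defines no analysis set, no denominator and no handling of drop-outs.

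**The concern.** A drop-out rule triggered by harm from the intervention makes the analysed cohort depend on the outcome being measured. If these patients are left out of the rates, the block looks safer than it was, and the error can run only one way for the events concerned. The Introduction postulates that side effects such as circulatory instability are less frequent under peripheral regional anaesthesia, and removal would favour that claim.

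There is also a conflict within section 8. A patient who has severe toxicity, is converted to general anaesthesia and then has the operation is a drop-out under the second paragraph and is retained under the third. Conversion is criterion 2 of the main objective (section 2), so the conflict reaches the primary rate as well as safety.

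**Working it through.** **No figure to reproduce.** The documents give no sample size and no toxicity, supplementation or conversion rate. Every count and risk below is an assumption chosen to show the mechanism. Intervals are exact (Clopper-Pearson) 95%.

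**Step 1: rate of the events that trigger drop-out.** With x such events among n patients given a block, the rate is x/n if all are counted. If the drop-outs are removed it is (x − x)/(n − x) = 0 for any x below n.

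| Assumed events | All counted | Drop-outs removed |
|---|---|---|
| 1 of 100 | 1.0% (0.03 to 5.45) | 0/99, upper limit 3.66% |
| 2 of 50 | 4.0% (0.49 to 13.71) | 0/48, upper limit 7.40% |
| 2 of 100 | 2.0% (0.24 to 7.04) | 0/98, upper limit 3.69% |
| 2 of 200 | 1.0% (0.12 to 3.57) | 0/198, upper limit 1.85% |
| 5 of 100 | 5.0% (1.64 to 11.28) | 0/95, upper limit 3.81% |

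In the last row the interval after removal excludes the 5% actually observed.

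**Step 2: wider event classes.** The zero does not carry over to these.
- All toxicity: section 7.1 also lists convulsions, coma and respiratory paralysis, and the list in section 8 is only by way of example, so their status is open. With 2 severe cardiovascular events and 3 other toxicity events in 100 patients, and only the first 2 removed, the rate falls from 5/100 = 5.0% to 3/98 = 3.06%.
- All severe events: with 4 in 100, of which 2 are toxicity drop-outs, the rate falls from 4.0% (1.10 to 9.93) to 2/98 = 2.04% (0.25 to 7.18).

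**Step 3: main objective.** Assume 20 of 100 patients supplemented or converted: 20.0% (12.67 to 29.18). Removing two toxicity patients gives 20/98 = 20.4% if neither was among the 20, or 18/98 = 18.4% if both were. Either shift is small against the interval. From a lower assumed base of 10 conversions in 100, removing two converted patients gives 8/98 = 8.16%. A large shift needs many removals: five converted patients removed gives 5/95 = 5.26%, but that presumes five toxicity drop-outs in 100.

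**Step 4: how often the rule would operate.** In 100 patients the chance of at least one event is 1 − (1 − p)^100. This is 9.5% at an assumed risk p of 0.1% and 63.4% at 1%. The chance of two or more is 1 − (1 − p)^100 − 100p(1 − p)^99, which is 0.5% and 26.4%. The two-event rows are therefore less likely than the one-event row at these risks.

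**Step 5: the texts side by side.** Section 8 says who is a drop-out and expressly retains one kind of patient. Sections 6.5, 7.3 and 7.4 govern visits, documentation and reporting. The SAP names tests and a summary measure. None of them says whether a drop-out is counted in a rate.

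**The case against.** The strongest reply is that nothing in either document removes drop-outs from the analysis. Section 8 lists reasons for drop-out and attaches no consequence for the data. The zero is then a tautology that follows from an assumption and is not an error found in the plan. Complications are documented with a causality statement, so the events can be recovered from the case report form. They are probably rare, and the main objective is barely touched.

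Much of this stands. Removal is implied and not stated, event capture is secured, and the effect on the main objective is small. What remains is that documentation does not set the denominator of a reported rate. Section 8 gives an assurance of retention to one kind of patient and withholds it from another, which makes removal the natural reading. As written, the choice could be made after the data are seen.

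A reader might infer more than the documents support:
- That the plan excludes harmed patients from analysis. It does not say so.
- That the whole toxicity rate, or the whole adverse-event rate, would be zero. Only the events that trigger drop-out are affected in that way (step 2).
- That a comparison of the block with another anaesthetic would be biased by a known amount. The SAP refers to two groups, but section 3 says only "This is a single-center prospective study", and no comparator is described.
- That mortality would be distorted by a known amount. The 5-20% in the Introduction is for ASA 3-4 patients, whereas section 5.1 sets no ASA limit, so it is not a figure for this cohort.

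**Conclusion.** The point holds as a gap in the rules that should be closed. On the natural reading of section 8, patients with severe cardiovascular toxicity leave the analysed cohort, and the rate of those events becomes 0% whatever its true value. The overall adverse-event rate would be understated by an amount that cannot be determined from the documents, and the supplementation or conversion rate would change little if such events are few. This rests on two assumptions: that drop-out means removal from analysis, and that at least one such event occurs. Neither is certain. The conflict between the second and third paragraphs of section 8 needs no assumption; the two must be reconciled. The undefined groups in the SAP are a separate matter and should be raised on their own.

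**What to change.** In section 8 and in the SAP, state that a complication caused by the intervention is never a reason to remove a patient from analysis. In the SAP, state that every enrolled patient in whom a block injection was started stays in the numerators and denominators of the safety, mortality and criterion 1 and 2 rates, and that every drop-out is listed with the reason. In section 8, reconcile the second and third paragraphs for a patient with severe toxicity who is converted to general anaesthesia, so that the analysis status of that patient is unambiguous.

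This concerns who is counted; it changes neither clinical care nor the endpoint. No new data are needed, because complications are already documented and daily visits are already planned. The one downside is that reported adverse-event rates may look slightly less favourable. Rules for withdrawn consent or late-found ineligibility may also be wanted, but they do not arise from the toxicity wording and are not part of this point.
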